### I. Hypotheses and Specific Aims:

1. Primary Aim: The primary aim of this study is to assess the clinical impact of a rapid multiplex PCR blood culture identification panel on time to optimal antimicrobial therapy when compared to conventional microbiological culture methods in children hospitalized in a low resource setting in Guatemala City.
2. Secondary aims:
  - a. To assess the impact of the blood culture identification panel on reduction in time to organism identification when compared to conventional microbiological culture methods
  - b. To assess the impact of the blood culture identification panel on time to effective antimicrobial therapy, mortality, length of stay, and ICU days.
3. We hypothesize that we will see an overall reduction in time to optimal antimicrobial therapy following implementation of the panel.

**II. Background and Significance:** There are high rates of blood culture positivity and antimicrobial resistance in Latin American countries, with high rates of broad-spectrum antimicrobial utilization. Based on our preliminary analysis of pediatric blood cultures at Hospital Roosevelt, the rates of carbapenem-resistant *Klebsiella* and *Acinetobacter* are 65% and 90%, respectively. Because of this, patients are often started empirically on broad-spectrum antibiotics until the organism and susceptibility results are identified. Rapid microbiology diagnostics, such as the Biofire Film Array BCID, have been shown to greatly impact clinical care in high-income countries. The best strategies for implementation and their potential clinical impact in low-middle income countries, however, have not been well defined. Hospital Roosevelt in Guatemala City is a 900-bed public hospital with 180 beds dedicated to pediatric patients. It serves 53% of children in the larger metropolitan area of Guatemala. Co-investigator has a long-standing relationship with Hospital Roosevelt and has partnered with Hospital Roosevelt on previous research studies. PI has an active research study at Hospital Roosevelt involving rapid diagnostics for Pneumococcal disease.

We have just completed a program evaluation to evaluate the current rates of positive blood cultures, time to pathogen identification, and time to effective and optimal antimicrobial therapy at Hospital Roosevelt Pediatric Department. Based on preliminary data, Hospital Roosevelt has an average of 800 pediatric blood cultures per month, with 5% positivity (roughly 45 positive pediatric blood cultures per month). The laboratory relies primarily on standard culture techniques for organism identification, which takes a median of 78 hours. With the implementation of a blood culture identification panel (BCID2), we expect to reduce the time to organism identification significantly, and therefore reduce time to optimal antimicrobial therapy. In order to facilitate this, we will couple the BCID2 results with antimicrobial stewardship that is already in place. Based on U.S. data conducted at our institution, implementation of Biofire Film Array BCID showed a reduction in time to optimal antimicrobial therapy to 27 hours on average with BCID plus antimicrobial stewardship.

### III. Preliminary Studies/Progress Report:

We have just completed a program evaluation at Hospital Roosevelt Pediatric Department in Guatemala City. We have retrospectively reviewed 99 consecutive available patient charts with positive blood cultures, and have analyzed current time to organism identification, time to effective and optimal antimicrobial therapy, as well as mortality rate. These will serve as historical controls. The current median time to pathogen identification is 78 hours with a range

of 34-122 hours. Only 37% of patients achieved optimal therapy; of those the median time to optimal therapy was 90 hours. Mortality rate among this cohort was 20%.

#### **IV. Research Methods**

##### **A. Outcome Measure(s):**

Primary Outcome:

1. Time to optimal antimicrobial therapy from the time of specimen receipt in the laboratory

Secondary Outcomes:

1. Time to pathogen identification from the time of specimen receipt
2. Time to effective antimicrobial therapy from the time of specimen receipt
3. Length of hospital stay
4. Mortality
5. Total antibiotic days (number of antibiotics per day X number of days)
6. Total ICU days

Exploratory outcomes:

1. Cost analysis
  - a. Grams of antibiotics used
  - b. Days of hospitalization
  - c. ICU days

##### **B. Description of Population to be Enrolled:**

- a. Pediatric patients birth to 18 years of age
- b. Patients on all pediatric and neonatal inpatient units at Roosevelt Hospital
- c. First positive blood cultures on admission or during hospitalization

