##### **C. Study Design and Research Methods**

- a. Currently the standard of care at Hospital Roosevelt is to perform standard blood culture on all specimens that are positive on the automated VIRTUO system. This occurs by trained lab technicians 24/7. Once there is colony growth on the plates via standard culture, the isolate is placed on the VITEK system for identification and susceptibility. This process has been analyzed in the program evaluation and will serve as historical controls.
- b. In this prospective study, we will implement the BioFire FilmArray blood culture identification panel (BCID2), which laboratory technicians will run simultaneously with standard culture after it flags positive on VIRTUO system. We will only run the BCID2 panel on those specimens that become positive during **normal working hours Monday-Friday from 7am to 1pm** due to the inability to staff the laboratory overnight and on weekends. **Those specimens that become positive from 12am to 7am will be run at 7am, as the panel can be run up to 24 hours from positivity per BioFire protocol.** Those that become positive in the evening from 1pm-11:59pm Monday-Thursday will not be run on the BCID2 and will serve as controls. All positive cultures (in both groups) will be plated on agar plates to confirm growth on culture and undergo susceptibility testing per standard current protocols.
- c. Physicians will be notified of panel results, as well as standard culture results per current laboratory protocol, which includes uploading results onto a webpage accessible to all physicians on their mobile device. **BCID2 results will additionally be reported to providers directly by telephone notification or in person by the study PI.** Standard culture results on control patients will be reported per standard protocol of webpage notification.
- d. Antimicrobial stewardship will be continued per current standard of care at Hospital Roosevelt. The Pediatric Infectious Disease fellows and attendings at Hospital Roosevelt review all positive cultures in the microbiology laboratory each morning,

and review results in person with the inpatient teams. **During this study, the local PI will serve as the antimicrobial steward and provide BCID2 results to physicians within 1 hour of notification. We will provide guideline-based recommendations for all BCID2 results to help standardize the stewardship process.**

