Rapid Blood Culture Identification Panel in Pediatric Patients in Guatemala

NCT05314816

Statistical Analysis Plan

v. 2/23/2023

Statistical Analysis Plan

Objective: to evaluate the clinical impact of the BioFire BCID2 panel in children with bacteremia in Guatemala.

Study Design: Pragmatic clinical trial comparing intervention to two different control groups. Intervention and concurrent control group allocated by time of blood culture positivity. Also comparing to historical controls.

Primary outcome: time to optimal antimicrobial therapy

Secondary outcomes:

- Time to effective antimicrobial therapy
- Time to pathogen identification
- Mortality
- Length of hospital stay
- Antibiotic days of therapy (DOT)
- Number of unique antibiotics
- Total ICU days

Definitions to consider:

Patient Group

Intervention= patient was enrolled in the intervention group and received the BCID2 intervention within 12h timeframe

Concurrent control= patient was enrolled in the study and did not receive the BCID2 intervention within 12h from blood culture positivity

- Weekday controls= Patient with positive blood culture from 1pm-11:59pm Mon-Thurs
- Weekend controls= Patient with positive blood culture from 1pm Fri- 11:59pm Sunday

Per protocol =patient received intervention based on original allocation.

- Per protocol intervention= Patient allocated to intervention based on timing of blood culture AND BCID2 was performed within 8h timeframe.
- Per protocol control= Patient allocated to control group based on timing of blood culture AND no BCID2 was performed.

Protocol deviation=Patient intended to remain in the allocated group, but there was an unintentional deviation from protocol.

- Protocol deviation intervention= BCID2 run between 8-12h in patient allocated to intervention.
- Protocol deviation control= BCID2 was sent clinically >12h from positive culture in patient allocated to control group OR patient originally allocated to intervention group but BCID2 was not performed.

Sub-groups

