Antibiotic days of therapy =Sum of antibiotics each day over 14-day period. For example if 2 antibiotics were each given over 5 days, this would count as 10 DOT.

Number of different antibiotics=Number of unique antibiotics given over the 14-day period.

Length of stay=date admitted to date patient left the study (date of death/discharge or lapse of 30 days). Censor at 30 days.

Total ICU days=date admitted in ICU to date transferred out or date of death/discharge. Censor at 30 days.

Time to death= Time from blood culture obtained to time of death.

Number of deaths within 24h of blood culture draw= Use time of death calculation above to determine the number of patients who died <24h

Overview of Analyses to perform:

- All interventions vs. all concurrent controls (including protocol deviations) vs. historical controls
 - Demographics
 - All outcomes (primary and all secondary endpoints)
 - Sensitivity analysis comparing weekday vs. weekend controls
- Per protocol controls vs. per protocol intervention (excluding protocol deviations)
 - Demographics
 - All outcomes (primary and all secondary endpoints)
- Clinician discretion (ITT) analysis (controls vs. interventions)

- Number of contaminants vs. true pathogens
- Time to optimal therapy
- Time to effective therapy
- Pathogen directed (Per protocol) analysis (controls vs. interventions)
 - Number of contaminants vs. true pathogens
 - Time to optimal therapy
 - Time to effective therapy
- Gram negatives only (on- and off- panel)
 - Demographics
 - Time to optimal therapy
 - Time to effective therapy
 - Mortality
- On-panel true pathogens only
 - Demographics
 - Time to optimal therapy
 - Time to effective therapy
 - Mortality
- On-panel Gram negatives only
 - Demographics
 - Time to optimal therapy
 - Time to effective therapy
 - Mortality
- True pathogens (on and off panel)
 - Demographics
 - Time to optimal therapy
 - Time to effective therapy
 - Mortality

Figure 1: CONSORT Diagram

Table 1: Patient Characteristics

*Wilcoxon test of medians

**chi-square test

Table 1A: Supplemental table with demographics from sub-groups.

	Per protocol Intervention	Per protocol Control	p-value	True on-panel pathogen Intervention	True on-panel Pathogen controls	p-value	All Gram negative (GN) Interv.	All GN control	p-value	All GN weekDAY controls	p-value (compare to GN interv.)	On-panel GN Interv.	On-panel GN control	p-value

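### Groups form when the bottle flags, but no child has to be alive and admitted then and time to death starts at the draw, so deaths before allocation enter the mortality comparison; net direction and size are unknown

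*Protocol*

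**What the plan says.** Eligibility (Protocol IV.B) has three elements: age, location and culture. Location is "Patients on all pediatric and neonatal inpatient units at Roosevelt Hospital" and culture is "First positive blood cultures on admission or during hospitalization". Neither is tied to a time point such as draw, flag or enrolment.

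The SAP's Study Design paragraph fixes when the groups form: "Intervention and concurrent control group allocated by time of blood culture positivity". The panel can follow the flag by some hours. Protocol IV.C states: "Those specimens that become positive from 12am to 7am will be run at 7am", a wait of up to 7 hours.

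The SAP's secondary outcome definitions start the death clock before allocation: "Time to death= Time from blood culture obtained to time of death". They add a count of very early deaths: "Number of deaths within 24h of blood culture draw= Use time of death calculation above to determine the number of patients who died <24h". Mortality as a proportion has no stated origin or window.

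The SAP's group definitions place among the control deviations a "patient originally allocated to intervention group but BCID2 was not performed". The first listed analysis, which covers all outcomes, is "All interventions vs. all concurrent controls (including protocol deviations) vs. historical controls".

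**The concern.** A child who dies between draw and flag has died before belonging to either group, and no result from the panel could have changed that outcome. Counting such deaths adds events that the intervention cannot influence.

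A second issue concerns children in the intervention window who die or go home before the panel is run. If the bottle is then not run, the SAP's deviation rule moves the child to control. A child with the same course in the control window was a control already. The movement is in one direction only, so it can distort the comparison as well as dilute it.

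Mortality is among the secondary aims (Protocol I), and Protocol IV.G raises a possible mortality benefit and wider implementation of the panel. A mortality difference from this trial would be read with that in mind.

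**Working it through.** The documents give no alpha, power or target effect for mortality, so there is no planned figure to reproduce. The group sizes agree across the SAP table shells: 112 + 23 = 135 intervention, 192 + 27 = 219 concurrent control, 135 + 219 = 354.

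**Inputs from the documents.** 135 and 219 children; 27 control deviations, not split between late clinical tests and panels never run; 20% mortality in the historical cohort (Protocol III), used here for both groups.

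**Assumed inputs.** The share *e* of deaths that come too early for the panel to act, 5% to 30%; a true risk ratio of 0.60 among the remaining deaths; two-sided alpha of 0.05; *k* deaths and *s* survivors moved to control because no panel was run.

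**1. Dilution, with early deaths kept in their flag-time group.**
Apparent risk ratio = *e* + (1 − *e*) × 0.60. For example, at *e* = 10% it is 0.10 + 0.90 × 0.60 = 0.64. Early deaths are 135 × 0.20 × *e* and 219 × 0.20 × *e*. Power uses the normal approximation for two proportions with pooled variance under the null. The last column restricts both groups to children without an early death, where the risk ratio is again 0.60.

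| *e* | Early deaths, intervention / control | Apparent risk ratio | Power, early deaths kept | Power, restricted set |
|---|---|---|---|---|
| 0% | 0 / 0 | 0.60 | 49.5% | 49.5% |
| 5% | 1.4 / 2.2 | 0.62 | 45% | 47% |
| 10% | 2.7 / 4.4 | 0.64 | 41% | 45% |
| 20% | 5.4 / 8.8 | 0.68 | 33% | 40% |
| 30% | 8.1 / 13.1 | 0.72 | 26% | 35% |

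**2. Reclassification, with no true effect.**
The intervention window originally held 135 + *k* + *s* children and the control window 219 − *k* − *s*, each with 20% mortality. After the move:

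- intervention deaths = 0.20 × (135 + *k* + *s*) − *k*, divided by 135
- control deaths = 0.20 × (219 − *k* − *s*) + *k*, divided by 219

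| *k* deaths | *s* survivors | Intervention | Control | Risk ratio |
|---|---|---|---|---|
| 1 | 0 | 26.2/135 = 19.4% | 44.6/219 = 20.4% | 0.95 |
| 3 | 0 | 24.6/135 = 18.2% | 46.2/219 = 21.1% | 0.86 |
| 7 | 0 | 21.4/135 = 15.9% | 49.4/219 = 22.6% | 0.70 |
| 3 | 12 | 27.0/135 = 20.0% | 43.8/219 = 20.0% | 1.00 |
| 0 | 6 | 28.2/135 = 20.9% | 42.6/219 = 19.5% | 1.07 |

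At 20% mortality, four moved survivors cancel one moved death. The row with 7 deaths is demanding: the window would hold 142 children and 0.20 × 142 = 28.4 deaths, so 7/28.4, about a quarter of the deaths, would come before the panel and every one of those bottles would go unrun. In every row *k* + *s* stays within the 27 control deviations, but the documents do not show how many of those 27 are unrun panels.

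**The case against.** A reader might infer that the plan has a built-in bias towards a mortality benefit. The documents do not support that. Protocol IV.C and IV.D describe testing that follows the specimen: technicians run the panel when the bottle flags, on all pediatric cultures positive in working hours, and no step checks whether the child is still alive. On that text a dead child's bottle may well be run, the child stays in the intervention group, and only dilution remains. If some bottles do go unrun, discharged survivors would offset moved deaths. This objection stands, and it is why no direction is claimed.

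It would also go too far to say that all mortality is counted from the draw. That origin is stated for time to death and for the 24-hour count; for the proportion who died, no origin is given.

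The plan also has partial safeguards. The location criterion can be read as requiring presence on a unit, but it names no moment. The SAP mentions exclusions at initial screening without giving criteria, so some such children may have been removed. The 24-hour count shows awareness of early deaths, but it is descriptive, and within 24 hours of the draw is not the same as before the flag. The per-protocol comparison takes moved children out of control but does not return them to intervention. The SAP's figure list offers positivity as a second time origin, but its heading limits this to time to optimal and effective therapy; the definition of time to death still uses the draw.

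Finally, mortality is one of several secondary outcomes and the primary outcome is not at issue here. That limits the weight of the point.

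**Conclusion.** The point holds as a mismatch between eligibility, allocation and time origin. Deaths before the flag can enter the mortality comparison, and no listed analysis takes them out. Their expected effect is dilution: under the assumptions above, a true risk ratio of 0.60 would appear as 0.64 if 10% of deaths were early and 0.68 if 20% were.

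Reclassification is conditional. It needs bottles left unrun because the child had died or left, which the documents neither state nor exclude. The risk ratios of 0.86 and 0.70 for 3 and 7 moved deaths take the extreme case in which every pre-run death moves and no survivor does; they are not estimates for this trial. The number of such children is not given, so the net direction and size remain unknown.

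**What to change.** In the SAP, for mortality and time to death:

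- Define the analysis set as children alive and admitted to a study unit when the bottle flags, applied identically to intervention, concurrent and historical groups.
- Start time to death at positivity, and state the origin and window for the mortality proportion.
- Analyse these children by flag-time window whether or not BCID2 was run, in place of the deviation rule. The eligibility condition alone is not enough: a child who flags at 1am, dies before 7am and is not run would meet it and still be counted as a control.
- Report deaths and discharges before the flag, by window, in the CONSORT diagram.
- State a same-day rule where only a discharge date is recorded.

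The SAP already carries group sizes, so the condition now acts as an analysis set and not as an enrolment criterion. The cost is mainly SAP wording, because the planned positivity-origin curves, which include the historical controls, largely need the same times. The downside is that a few children leave the mortality comparison, and its result applies to children alive and admitted at positivity.

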##### **C. Study Design and Research Methods**

- a. Currently the standard of care at Hospital Roosevelt is to perform standard blood culture on all specimens that are positive on the automated VIRTUO system. This occurs by trained lab technicians 24/7. Once there is colony growth on the plates via standard culture, the isolate is placed on the VITEK system for identification and susceptibility. This process has been analyzed in the program evaluation and will serve as historical controls.
- b. In this prospective study, we will implement the BioFire FilmArray blood culture identification panel (BCID2), which laboratory technicians will run simultaneously with standard culture after it flags positive on VIRTUO system. We will only run the BCID2 panel on those specimens that become positive during **normal working hours Monday-Friday from 7am to 1pm** due to the inability to staff the laboratory overnight and on weekends. **Those specimens that become positive from 12am to 7am will be run at 7am, as the panel can be run up to 24 hours from positivity per BioFire protocol.** Those that become positive in the evening from 1pm-11:59pm Monday-Thursday will not be run on the BCID2 and will serve as controls. All positive cultures (in both groups) will be plated on agar plates to confirm growth on culture and undergo susceptibility testing per standard current protocols.
- c. Physicians will be notified of panel results, as well as standard culture results per current laboratory protocol, which includes uploading results onto a webpage accessible to all physicians on their mobile device. **BCID2 results will additionally be reported to providers directly by telephone notification or in person by the study PI.** Standard culture results on control patients will be reported per standard protocol of webpage notification.
- d. Antimicrobial stewardship will be continued per current standard of care at Hospital Roosevelt. The Pediatric Infectious Disease fellows and attendings at Hospital Roosevelt review all positive cultures in the microbiology laboratory each morning,

and review results in person with the inpatient teams. **During this study, the local PI will serve as the antimicrobial steward and provide BCID2 results to physicians within 1 hour of notification. We will provide guideline-based recommendations for all BCID2 results to help standardize the stewardship process.**

- e. We will compare time to optimal antimicrobial therapy (primary outcome), as well as secondary outcome measures, between the intervention group and the 2 control groups (historical controls, as well as concurrent controls).

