**F. Data Analysis Plan:** Hospital Roosevelt has 800 pediatric blood cultures processed monthly (with about 5% positivity). Based on preliminary data, only 37% of patients with positive blood cultures received optimal therapy based on predefined consensus guidelines. Of those who receive optimal therapy, the median time to therapy is 90 hours. With the addition of a blood culture identification panel, we expect to see a reduction in time to optimal antimicrobial therapy to 30 hours. This estimate is based on U.S. data conducted at our institution showing a reduction to 27 hours on average with BCID plus antimicrobial stewardship.

Target Enrollment: 100 patients over 4 month study period

**G. Summarize Knowledge to be Gained:** This study is important to evaluate the impact that rapid multiplex blood culture identification PCR panels have on improving clinical outcomes in low-middle income countries such as Guatemala. It has shown significant impact in reduction in time to optimal antimicrobial therapy in high-income countries. In countries such as Guatemala, with higher rates of antimicrobial resistance and broad-spectrum antimicrobial usage, the potential impact is greater and could lead to a mortality benefit. If a significant clinical impact is observed, we would advocate for continued use of the panel at Hospital Roosevelt, as well as 24/7 implementation if a significant difference is seen between the intervention and prospective control group. This could be translatable to other low-middle income countries.

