Clinician discretion (Intention to treat analysis (ITT))=effective and optimal therapy determined based on whether **treating physicians** considered the pathogen real or a contaminant. Optimal therapy allowed additional antibiotics if the treating team was also treating for other syndromic diagnoses, such as culture-negative sepsis (if pathogen detected deemed to be a contaminant), nosocomial pneumonia, etc. if called out in diagnoses. Definitions created for optimal therapy for nosocomial pneumonia, culture-negative sepsis, etc.

- Time to effective therapy in ITT:
 - Time from blood culture received in lab (time 0) to effective therapy
 - Time from blood culture positivity (time 0) to effective therapy
- Time to optimal therapy in ITT:
 - Time from blood culture received in lab (time 0) to effective therapy
 - Time from blood culture positivity (time 0) to effective therapy

Pathogen directed (Per protocol analysis) =effective and optimal therapy based on **strict definitions** for real pathogen or contaminant created by study team. Strict optimal antibiotic definitions without allowing for additional antibiotics for culture-negative sepsis or nosocomial pneumonia, etc. Does allow for additional antibiotics for clear other indications (pyelonephritis, CAP, dacrocystitis, intra-abdominal abscess, etc.) or another organism isolated (excluding urine and trach cultures). Not allowing for more controversial diagnoses such as sepsis or nosocomial pneumonia.

- Time to effective therapy in per protocol:
 - Time from blood culture received in lab (time 0) to effective therapy
 - Time from blood culture positivity (time 0) to effective therapy
- Time to optimal therapy in per protocol:
 - Time from blood culture received in lab (time 0) to effective therapy
 - Time from blood culture positivity (time 0) to effective therapy

Secondary outcomes

Time to pathogen identification= Time from time of blood culture receipt in lab (time 0) to identification of a pathogen. For control patients, this is the time to Vitek. For intervention patients, this is the time to BCID2 if the BCID2 was positive for an on-panel pathogen or time to vitek if the BCID2 was negative.

- Control: time to Vitek
- Intervention:
 - If BCID2 positive → calculate time to BCID2 result
 - If BCID2 negative → calculate time to Vitek

Total antibiotic days=all days that patient was on antibiotics (any dose of antibiotic) from date that blood culture was drawn. Capped at 14 days or date of death.

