Table 3B: For non-NICU patients only

Table 3C: Table of outcomes with sub-groups for all units

	Per protocol interventions	Per protocol Controls	p-value	All Gram negative interventions	All Gram negative controls	p-value	All GN weekDAY controls	p-value (compare to GN interv.)	True on-panel pathogens interventions	True on-panel pathogens controls	p-value	On-panel Gram neg interv	On-panel Gram neg control	p-value
--	----------------------------	-----------------------	---------	---------------------------------	----------------------------	---------	-------------------------	---------------------------------	---------------------------------------	----------------------------------	---------	--------------------------	---------------------------	---------

Median total antibiotic days (XX days)													
Median antibiotics DOT													
Number of unique antibiotics in 14-day period													

Table 4: BCID2/Vitek discrepancies in intervention patients

	Number of patients (N, %)
BCID2/Vitek agreed	
BCID2/Vitek disagreed	
BCID2 positive, Vitek negative	
BCID2 negative, Vitek positive	
Species misidentification	
Resistance gene did not match susceptibility	
Organism not on panel	

Other parameters:

- Look at distribution (median with IQR) of time between BCID2 result and team notification (only for intervention patients).
- Look at distribution (median with IQR) of time between BCID2 execution and team notification (only for intervention patients).
- Age distribution and gender between those excluded via initial screening and those included (initially enrolled).

Figures: Kaplan Meier curves for time to optimal and time to effective therapy (using both intention to treat AND per protocol analyses)

1st way- time of blood culture draw as time 0

2nd way- time of blood culture positivity as time 0

Figure 1: Compare interventions vs. concurrent controls vs. Historical controls (all pathogens)

Figure 1A: time to effective therapy ITT

Figure 1B: time to effective therapy per protocol

Figure 1C: time to optimal therapy ITT

Figure 1D: time to optimal therapy per protocol

Figure 1E: time to death (deaths only)

Figure 2: Compare interventions vs. concurrent controls vs. Historical controls (Gram negative rods on-panel and off-panel)

Figure 3: Compare interventions vs. concurrent controls vs. Historical controls (True on-panel pathogens only)

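### Time to optimal therapy is tested against two unranked control groups under two unranked scorings, with no alpha or multiplicity rule; if any significant result counts, the false-positive rate is about 13–16%, not 5%.

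*Protocol*

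**What the plan says.** - **Outcome and clock.** Protocol IV.A names one primary outcome, time to optimal therapy, counted from receipt of the specimen in the laboratory. The SAP definition under Primary outcomes uses the same start.
- **Comparators.** Protocol IV.C, item e, compares this outcome "between the intervention group and the 2 control groups (historical controls, as well as concurrent controls"). The SAP's Overview of Analyses lists "All interventions vs. all concurrent controls (including protocol deviations) vs. historical controls". No order is given in either place.
- **Scorings.** The SAP defines optimal therapy once by clinician discretion (labelled ITT) and once by strict pathogen-directed rules (labelled per protocol). Both appear in the Overview, and the Kaplan-Meier curves are drawn "using both intention to treat AND per protocol analyses".
- **Other clocks.** Under each scoring the SAP lists laboratory receipt and, beside it, "Time from blood culture positivity (time 0) to effective therapy". The Figures section uses blood draw and positivity. None of these additions is labelled a sensitivity analysis.
- **Consequence.** Protocol IV.G states: "If a significant clinical impact is observed, we would advocate for continued use of the panel at Hospital Roosevelt". The same sentence makes 24/7 use depend on a significant difference from the prospective control group.
- **Error control.** Neither document gives an alpha, a sidedness or a multiplicity rule. The design figures in Protocol IV.F are an expectation ("we expect to see a reduction in time to optimal antimicrobial therapy to 30 hours") and "Target Enrollment: 100 patients over 4 month study period".

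**The concern.** There is one primary outcome but no primary analysis. The versions can disagree for real reasons. The historical and concurrent controls come from different periods. The two scorings treat contaminants differently, and they differ on whether additional antibiotics for conditions such as culture-negative sepsis or nosocomial pneumonia are compatible with optimal therapy. If one version is significant and another is not, nothing in the plan says which one answers the primary aim. A reader of the final report could not tell whether the headline was the intended test or the most favourable of several. A nominal 5% level would not describe the chance of a false claim, and Protocol IV.G attaches policy advocacy to significance.

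**Working it through.** **The plan's own figure.** No error rate, power or alpha is stated, and the target of 100 has no stated derivation, so there is nothing to reproduce. I assume each test is two-sided at 0.05.

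**Inputs.** Group sizes come from the SAP table shells: intervention 135, concurrent control 219, historical control 99. I assume a correlation between test statistics of 0.5–0.9 for the two scorings and 0.8–0.95 for the receipt and positivity clocks. The documents give neither.

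**Correlation between the two control comparisons.** They share the intervention arm, so

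ρ = (1/135) / √[(1/135 + 1/219)(1/135 + 1/99)] = 0.00741 / √(0.01197 × 0.01751) = 0.51.

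**Upper bounds, if tests were independent:** 1 − 0.95^k.
- k = 2: 9.75%
- k = 4: 18.5%
- k = 8: 33.7%

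These are too high because the tests share patients.

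**With correlation.** I simulated multivariate normal test statistics under no effect and no bias. The correlation matrix is the product of the control, scoring and clock correlations. The result is the proportion of draws with at least one |Z| > 1.96.

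| Tests counted | k | Either direction (nominal 5%) | In the panel's favour (nominal 2.5%) |
|---|---|---|---|
| Two comparators, one scoring, receipt clock | 2 | 9.0% | 4.5% |
| Two comparators × two scorings, receipt clock | 4 | 13–16% | 6–8% |
| The same, with the positivity clock added | 8 | 16–24% | 8–12% |
| 24/7 decision: concurrent controls, two scorings, receipt clock | 2 | 7–9% | 3.5–4.6% |
| 24/7 decision, with the positivity clock added | 4 | 9–14% | 4.5–7% |

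The lower end of each range has the highest assumed correlations. The four receipt-clock tests therefore run at about 2.5 to 3.2 times nominal (12.5/5 to 16.1/5), in either direction or in the panel's favour. The 24/7 decision on the receipt clock runs at about 1.4 to 1.8 times nominal (7.0/5 to 9.1/5).

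**Sensitivity to group size.** With 50, 50 and 99 patients, ρ becomes 0.58 and the four-test range is 12–16%.

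The blood-draw clock is not in these counts. The calculation covers multiplicity only, not bias from allocation by time of day or from historical controls.

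**A wording conflict found on the way.** In the SAP's lists for both scorings, every line under the time-to-optimal-therapy heading ends at effective therapy. That contradicts the SAP's own definition of time to optimal therapy, which ends at the first dose of an optimal antibiotic. I have read these lines as meant for optimal therapy.

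**The case against.** Much of the plan is more ordered than a long list of analyses suggests.

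- **The clock is fixed.** Protocol IV.A and the SAP definition agree on laboratory receipt. A reader might infer that the clock starts are unranked and count eight primary tests. The documents do not support that. What stands is that positivity and draw are added without a label, and that the Figures section omits the defined clock.
- **The weekday and weekend controls, per-protocol set and subgroups are not rival primary tests.** The Overview calls the first "Sensitivity analysis comparing weekday vs. weekend controls". Excluding deviations is a conventional supportive analysis, and the organism groups come under a sub-group heading. A count of 16 or 20 primary tests is not supported.
- **Time to effective therapy is not a second primary outcome.** It appears under the SAP heading Primary outcomes, but the SAP's opening list and Protocol IV.A both make it secondary.
- **The comparator is partly ordered.** The SAP's Study Design adds the historical group as a further comparison, and the 24/7 statement names the prospective controls only. This stands for the 24/7 decision. It does not rank the comparators for the primary aim or for continued use.
- **Protocol IV.G is a statement of knowledge to be gained, not a decision rule.** It does not say that one significant result among several is enough. That is fair, so the rates above are conditional. But it names no outcome, comparator or scoring, and nothing excludes that reading.
- **Advocacy needs a favourable result.** Counting one direction halves the rates, but it halves the nominal rate too, so the inflation is about the same.

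One further inference should be resisted. The SAP, dated 23 February 2023, already carries group sizes. That shows the choice was still open once those were known; it does not show that outcomes had been seen by group.

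**Conclusion.** The point holds in a limited form. The primary outcome has two unranked comparators and two unranked scorings, with no alpha or multiplicity rule, and further clock starts are listed without a label. If any significant result counts, the false-positive rate is about 13–16% on the receipt clock, and 16–24% only if the positivity clock is also allowed to count. For 24/7 use it is about 7–9%, so a claim that every advocacy decision carries several times the nominal error would be too strong. All of this rests on an assumed two-sided 5% level and on assumed correlations between scorings and clocks. The absence of a primary analysis does not depend on those assumptions.

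**What to change.** In the SAP:

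1. Name one primary analysis: intervention versus concurrent controls grouped by allocation window, time to optimal therapy from laboratory receipt, one scoring named with its reason, two-sided 5%. Keep laboratory receipt; moving the primary clock to positivity would change the protocol-defined endpoint after enrolment.
2. Test the historical comparison second, and only if the first is significant. This fixed order keeps the overall error at 5% without splitting alpha. Keeping all four receipt-clock tests as equals would instead need 0.05/4 = 0.0125 each under Bonferroni.
3. Label the other scoring, the positivity and draw clocks, the per-protocol set and the subgroups as sensitivity or exploratory, reported with estimates and confidence intervals.
4. Correct the lines under time to optimal therapy that end at effective therapy.

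In Protocol IV.G, or by a statement in the SAP, tie the advocacy statement to the named test.

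Fix the choice before those making it see outcomes by group, or disclose that it was made afterwards.

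The cost is mainly wording, with no new data. Grouping by allocation window also means re-deriving the analysis groups, because the SAP counts patients allocated to intervention whose panel was not run as controls. The downside is that the headline then rests on one result, which may be less favourable than another version.
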